4.0 ENDPOINTS

4.1 Primary Endpoint

The primary endpoint is Acute Procedural Success (APS). This is defined as successful implantation of the MitraClip device with resulting MR severity of 2+ or less upon discharge Echocardiogram (30-day echocardiogram will be used if discharge is unavailable or uninterpretable). Subjects who die or undergo mitral valve surgery before discharge are an APS failure

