3.2 Overall Flow of the Study and Follow-up Schedule

[figure not shown]
Enrolled patients that receive a MitraClip implant should undergo study follow-up per standard of care. Follow-up data on clinical assessment should be submitted for a 30-day visit, 6-month visit or phone call and 12-month visit. Echocardiograms are required to be submitted for the baseline, discharge, 30-day and 12-month time points. All Echocardiograms conducted during the study period (required by protocol or not) will be collected by the Sponsor (see **Table 2** for the Clinical Assessment Schedule). Patients that have an attempted procedure, but no MitraClip implant will be followed for 30 days only.

The first 220 European patients treated with the MitraClip XTR in *the MitraClip EXPAND Study* with evaluable APS data will be included in the XTR PMCF Study as described in Appendix 1.

Subjects with evaluable echocardiograms may be selected for a more detailed assessment by an independent core lab. Pre-defined criteria will be used to identify eligible subjects for this assessment. A minimum of 100 subjects will be randomly selected from this eligible population.

Figure 3 outlines the flow of the Study.

Figure 3: Study Flow

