6.4 Subject Follow-up

Follow-up is conducted per standard of care visits shown below. All follow-up assessment, visit or phone, should include a review for adverse events occurring since the last visit. Results from the KCCQ survey are required to be recorded and submitted at the 30-day and 12-month visits. Visit should be scheduled relative to the date of the MitraClip Procedure. If a 6-minute walk test is conducted as standard of and was conducted at baseline; results for 6-minute walk test at 30day and 12-months visits will be collected in the EXPAND Study.

Visits at:

- 30 days (30 days -14 days / +60 days)
- 12 months (365 days - 30 days / +90 days)

Phone call or visit at:

- 6 months (180 days - 30 days / +90 days)

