4.3 Success Criteria

The MitraClip XTR PMCF Study will be successful if the lower one-sided 95% confidence interval (CI) of the observed APS rate for the study is greater than the Performance Goal (PG) of 80.7%.

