9.4.4 Procedures for Accounting for Missing, Unused or Spurious Data

If Echocardiography assessed MR severity at discharge is unavailable or cannot be assessed, the 30-day value will be used to assess APS. All analyses will be based on available data with missing data excluded. Any unused or spurious data will be noted as appropriate

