2.8 Handling of Missing Data

All analyses will be based on available data. Missing data will not be imputed. Any unused or spurious data will be documented as appropriate in the clinical report. For APS endpoint, a 30-day echocardiogram will be used if discharge is unavailable or uninterpretable.

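### When APS falls back on a 30-day echo that may be as late as day 90, the rule making death or mitral valve surgery a failure still stops at discharge

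*Protocol*

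**What the plan says.** **Definition.** PMCF protocol (EXPAND Appendix I) section 4.1 requires a successful implant and MR of 2+ or less at discharge, with the fallback "30-day echocardiogram will be used if discharge is unavailable or uninterpretable". It then states: "Subjects who die or undergo mitral valve surgery before discharge are an APS failure". The PMCF protocol summary and section 9.1, EXPAND section 4.2 and SAP section 1.4.2 carry the same two elements. None extends the failure rule beyond discharge.

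**Window.** EXPAND section 6.4 sets the visit at "30 days (30 days -14 days / +60 days"), counted from the procedure. The PMCF follow-up table gives the same window.

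**Missing data.** PMCF section 9.4.4 repeats that "the 30-day value will be used to assess APS", says nothing about events before that echo, and continues: "All analyses will be based on available data with missing data excluded". SAP section 2.8 adds "Missing data will not be imputed".

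**Who is counted.** EXPAND section 3.2 takes the first 220 European XTR patients "with evaluable APS data will be included in the XTR PMCF Study".

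**Success rule.** Under PMCF section 4.3 the study succeeds if the lower one-sided 95% confidence limit for APS "is greater than the Performance Goal (PG) of 80.7"%.

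**The concern.** The fallback moves the time of assessment without moving the failure rule, which leaves an interval of up to about three months in which neither arm of the definition works as intended.

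- **Death after discharge, before the fallback echo.** There is no MR grade and no failure rule applies. The subject is missing, and selection on evaluable APS keeps the subject out of the 220.
- **Mitral valve surgery in the same interval, then a 30-day echo.** An MR grade exists, so the text scores it. The valve being graded has been operated on, and the result may count as a success for the clip.

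Whether a fallback subject is evaluable therefore depends on surviving to the echo. PMCF section 2.2 justifies APS as a combined safety and performance measure because it captures death and re-intervention, so the gap weakens the property for which the endpoint was chosen. At stake is a pass/fail comparison with a fixed goal.

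**Working it through.** **Inputs from the documents**
- Goal 80.7% (PMCF 4.3); one-sided type I error 0.05 and a minimum of 220 subjects (PMCF 9.3); exact test (PMCF 9.4.1).
- 30-day window −14/+60 days (EXPAND 6.4; PMCF follow-up table).
- German TRAMI registry, for scale: 2.4% in-hospital and 4.5% 30-day mortality (EXPAND Appendix IV).

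**Inputs assumed, because the documents give none**
- Share of discharge echoes unusable: 5% to 15%.
- Risk of death or mitral valve surgery between discharge and the fallback echo: 2.1% to 5%. The lower value is registry mortality only, 4.5% − 2.4% = 2.1 points to day 30. The upper value allows for surgery and for the window running past day 30; no 90-day figure is given.

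**1. The plan's own figure.** The expected APS rate and the power are redacted, so 220 cannot be reproduced. It is compatible with several choices, for example 87% and 80% power, or 88% and 90% power (exact n = 217 in both cases).

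**2. Latest fallback echo.** 30 − 14 = day 16; 30 + 60 = day 90.

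**3. Pass mark at exactly n = 220.** The smallest x with P(X ≥ x | n = 220, p = 0.807) ≤ 0.05 is 188, where the tail probability is 0.041. One-sided 95% Clopper-Pearson lower limits:

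| Result | Rate | Lower limit | Against 80.7% |
|---|---|---|---|
| 188/220 | 85.45% | 80.96% | pass |
| 187/220 | 85.00% | 80.46% | fail |
| 188/221 | 85.07% | 80.55% | fail |
| 188/222 | 84.68% | 80.14% | fail |

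The row 188/221 is a borderline pass with one excluded subject restored as a failure. The row 187/220 is the same pass with one operated valve re-scored from success to failure.

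**4. Expected number affected** = 220 × share unusable × event risk.
- Low: 220 × 0.05 × 0.021 = 0.23
- High: 220 × 0.15 × 0.05 = 1.65

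As a share of all subjects: 0.05 × 0.021 = 0.1% to 0.15 × 0.05 = 0.75%.

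**5. Type I error of the 188/220 rule.** Suppose a share q of all subjects is excluded, all of them would count as failures under the extended rule, and true APS on that basis is 80.7%. The success rate among evaluable subjects is then 0.807/(1 − q).

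| q | Evaluable rate | P(X ≥ 188) |
|---|---|---|
| 0 | 80.70% | 0.041 |
| 0.25% | 80.90% | 0.048 |
| 0.5% | 81.11% | 0.056 |
| 0.75% | 81.31% | 0.065 |

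The assumed range of q, 0.1% to 0.75%, runs from below the nominal 0.05 to modestly above it.

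**6. How often the boundary is in play.** The chance of exactly 188 or 189 successes in 220 is 9% if true APS is 88% and 2% if it is 90%.

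**The case against.** **Excluded deaths need not be failures.** A reader might infer that the fallback removes only failures. The documents do not support that. Under the existing definition, a subject with MR 2+ or less on a readable discharge echo who dies on day 20 is a success. Deaths excluded for want of a discharge echo may therefore include subjects who were successes at discharge. This stands: exclusion depends on a bad outcome and tends to favour passing, but no more than that. Step 5 is correspondingly an upper case, since it scores every excluded subject as a failure.

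**Surgery does not imply exclusion.** A reader might also infer that subjects operated on after discharge are dropped. They are dropped only if they have no 30-day echo; otherwise their operated valve is graded.

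**The late echo can work the other way.** MR may recur before day 90 and turn a discharge success into a failure. That is true of fallback subjects who are scored, but it does not answer the handling of death or surgery.

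**Hidden text and conflicting rules.** PMCF section 9.2 shows no text, and parts of 9.3 and 9.4.1 are redacted, so a rule there cannot be ruled out. On whether an unevaluable subject's place is filled, EXPAND section 5.10 says subjects are not replaced, and PMCF section 3.2 includes patients once the XTR procedure is complete. EXPAND section 3.2 nevertheless selects on evaluable APS, and PMCF section 9.4.4 excludes missing values. The visible definition stops at discharge wherever it appears; if another rule exists, the definition should carry it.

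**Extending the rule creates an asymmetry.** Fallback subjects would face a longer event window than those with a discharge echo, and comparability with the historical APS rate could weaken slightly. This is a real cost, but confined to the few subjects who use the fallback.

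**Limited reach.** EXPAND endpoints are descriptive, and post-discharge deaths still appear under MAE and all-cause mortality. Only the PMCF verdict could change.

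**Conclusion.** The point holds in a limited form. As visibly written, APS for subjects without a usable discharge echo is judged as late as day 90, while the failure rule ends at discharge. Deaths in between leave the analysis, and operated valves can be graded as though the result belonged to the clip. The likely direction favours meeting the 80.7% goal.

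The size is small: roughly 0.2 to 1.7 subjects per 220. That range rests on the assumed 5–15% of unusable echoes and 2.1–5% event risk; only the 2.1% comes from figures in the documents. The pass mark of 188 is derived here, not stated in the plan, and applies only if exactly 220 subjects are analysed, whereas the plan says a minimum of 220. One subject can reverse the verdict at that boundary, but away from it the conclusion would not change. This is a cheap improvement, not a threat to the study.

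**What to change.** In PMCF sections 4.1, 9.1 and 9.4.4, and for consistency EXPAND section 4.2 and SAP sections 1.4.2 and 2.8, add: when the 30-day echo is used for APS, death or mitral valve surgery before that echo is an APS failure, and the subject is evaluable.

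Also:
- report how many APS results used the fallback echo and how many subjects were unevaluable;
- add a sensitivity analysis counting unevaluable subjects as failures;
- leave repeat mitral intervention (such as a second clip) out of the primary definition, which does not count it even before discharge. Report it among fallback subjects or handle it in the sensitivity analysis.

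The cost is one sentence and two counts, plus one extra analysis. Deaths and cardiovascular events are already collected through 12 months. APS may come out a fraction of a point lower, and fallback subjects are held to a somewhat longer event window than the rest.

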4.2 Clinical Endpoints

Clinical Endpoints will be assessed at each study time point, all data reported at the corresponding study visit will be included for the study time point.

- Major Adverse Events (MAE): defined as a composite of CEC adjudicated all-cause Death, Myocardial Infarction, Stroke, or non-elective CV surgery for device related complications
- MR Severity
- Device Related Adverse Events (including mitral valve stenosis, device embolization, single leaflet device attachment (SLDA), iatrogenic atrial septal defect, myocardial perforation, or the need for mitral valve replacement instead of repair due at least in part to the MitraClip procedure or the presence of the MitraClip device)
- All-cause mortality
- Recurrent heart failure hospitalization
- New York Heart Association (NYHA) functional class improvement

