4.0 STUDY ENDPOINTS

4.1 Safety and Performance Measures

- Safety
The assessment of safety will include all occurrences through 30 days post procedure.
Occurrence of Major Adverse Events (MAE) at 30 days
MAE is defined as a composite of all-cause Death, Myocardial Infarction, Stroke, or non-elective Cardiovascular (CV) surgery for device related complications (CEC adjudicated).
- Performance
The assessment of performance measures will include all data reported at 30-day visits for this study.
MR Reduction to $\leq 2+$ at 30 days

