4.3 Clinical Measures

(Discharge, 1, 6 and 12 months):

- All-cause Mortality
- Heart Failure Hospitalization
- MAE as defined above
- Device-Related Complications as defined above

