3.2 Adverse Events

All of the adverse events (AEs), serious adverse events (SAEs), adverse device effects (ADEs) and serious adverse device effects (SADEs) will be summarized using number of events, the percentage of subjects with events, and event rates per MedDRA coding.

All CEC adjudicated adverse events up to 30 days post index procedure will also be summarized using number of events, the percentage of subjects with events, and event rates.

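### The PMCF by-visit rule ends its 30-day event count anywhere from day 16 to day 90, while EXPAND stops at day 30, so shared subjects can get different 30-day MAE counts

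*Protocol*

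**What the plan says.** **PMCF (Protocol Appendix I).** Section 4.2 puts one rule ahead of all its clinical endpoints: "all data reported at the corresponding study visit will be included for the study time point". The list mixes measurements (MR severity, NYHA class) with events (MAE, all-cause mortality, device-related adverse events, recurrent heart failure hospitalisation). Table 1 in PMCF 6.4 gives the 30-day visit a window of -14/+60 days.

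**EXPAND.** Protocol 4.1 separates the two kinds of endpoint. For safety: "The assessment of safety will include all occurrences through 30 days post procedure". For MR: "The assessment of performance measures will include all data reported at 30-day visits for this study". SAP 1.4.1 repeats both rules, and SAP 3.2 adds: "All CEC adjudicated adverse events up to 30 days post index procedure will also be summarized". Protocol 6.4 gives the same visit window as PMCF: "30 days (30 days -14 days / +60 days". Protocol 4.3 lists MAE again at 1 month ("MAE as defined above") without a further counting rule.

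**Overlap.** The MAE components are the same in both studies: death, myocardial infarction, stroke, and non-elective cardiovascular surgery for device-related complications, all CEC adjudicated. Protocol 3.2 draws the PMCF subjects from EXPAND.

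No section reconciles the two rules.

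**The concern.** EXPAND applies a calendar rule to events and a visit rule to echocardiographic measurements. PMCF applies the visit rule to both. A visit rule suits MR grade, which exists only when an echocardiogram is done. Applied to events, it gives subjects unequal exposure under one 30-day label, so the count depends partly on when subjects happened to attend.

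The rule also leaves cases open. It does not say where to place a death before the visit, an event in a subject who misses the visit, or an event reported between visits. Death is itself an MAE component.

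PMCF data are meant to meet the CE-mark follow-up requirement, and PMCF 1.1 says adverse events through 12 months will further confirm safety. PMCF 2.1 cites a 30-day MAE rate from an earlier registry, so readers are likely to compare like-labelled figures. Two different 30-day MAE counts for the same subjects would need explaining.

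**Working it through.** **Plan's own figures.** The plan gives no expected MAE rate, so there is none to reproduce. The PMCF minimum of 220 subjects is sized on APS. Its assumed APS rate is redacted, and nothing below depends on it.

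**Step 1: the cut-off dates.** Earliest 30-day visit: 30 - 14 = day 16. Latest: 30 + 60 = day 90. PMCF 7.3.1 starts adverse event reporting when the delivery system enters the femoral vein. The period counted is therefore day 0 to the visit date, with the visit between day 16 and day 90.

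**Step 2: how one event is classified.**
- First MAE on day 45, visit on day 60: a 30-day event in PMCF, not in EXPAND.
- First MAE on day 25, visit on day 16: within 30 days in EXPAND. In PMCF it belongs to the next contact, because follow-up "should include a review for adverse events occurring since the last visit" (Protocol 6.4).
- First MAE on day 10, visit on any day from 16 to 90: the same in both.

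**Step 3: illustrative size, death only.** The 30-day MAE rates that Appendix IV gives with a definition use different composites, so I use all-cause death. Inputs from Protocol Appendix IV:
- German registry: 4.5% at 30 days, 20.3% at 1 year.
- US registry, patients linked to claims: 5.2% at 30 days, 25.8% at 1 year.

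Assumptions (mine): constant hazard from day 30 to day 365, constant hazard from day 0 to day 30, every visit on the stated day, and a death before the visit assigned to the 30-day time point.

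Daily hazard after day 30, h = ln[(1 - m30)/(1 - m365)]/335:
- German: ln(0.955/0.797)/335 = 0.000540
- US: ln(0.948/0.742)/335 = 0.000731

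Cumulative death at day t > 30: 1 - (1 - m30) × exp[-h(t - 30)].
- German, day 60: 1 - 0.955 × exp(-30 × 0.000540) = 6.0%
- German, day 90: 1 - 0.955 × exp(-60 × 0.000540) = 7.5%
- US, day 90: 1 - 0.948 × exp(-60 × 0.000731) = 9.3%

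Cumulative death at day 16: 1 - (1 - m30)^(16/30), which is 2.4% (German) and 2.8% (US).

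| All visits on day | German | Deaths per 220 | US | Deaths per 220 |
|---|---|---|---|---|
| 16 | 2.4% | 5.3 | 2.8% | 6.2 |
| 30 (fixed cut-off) | 4.5% | 9.9 | 5.2% | 11.4 |
| 45 | 5.3% | 11.6 | 6.2% | 13.7 |
| 60 | 6.0% | 13.3 | 7.3% | 16.0 |
| 90 | 7.5% | 16.6 | 9.3% | 20.4 |

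Against the day-30 count, visits all on day 90 would add about 7 deaths per 220 (16.6 - 9.9, German) or 9 (20.4 - 11.4, US).

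**The case against.** The best reply is that little depends on this. PMCF success rests on APS against a performance goal of 80.7%, and MAE is only summarised (PMCF 9.4.2). PMCF 9.4 names all-cause mortality as its example for Kaplan-Meier analysis, and such a curve can be read at day 30, so death may be the endpoint least exposed. Most visits may cluster near day 30. PMCF defines no separately titled 30-day MAE rate, and nothing visible shows that EXPAND will report MAE for the PMCF subset alone.

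Most of this stands, and it limits the point to a wording repair. It does not remove it. PMCF 9.4 does not assign MAE to Kaplan-Meier, and PMCF 4.2 still fixes the time point by visit for every clinical endpoint. The 30-day label follows from that section's reference to each study time point and from the schedule in PMCF 6.4.

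A reader might also infer four stronger things that the documents do not support:
- **That PMCF omits events before day 16.** Counting starts at the procedure; only the end date varies.
- **That the two counts must differ.** They differ only if a shared subject has a first MAE between day 30 and a later visit, or between an early visit and day 30.
- **That EXPAND reports 30-day MAE as a simple proportion and so mishandles subjects last seen before day 30.** SAP 2.3 sends all endpoints to SAP 2.2, which holds both proportions and Kaplan-Meier with censoring, and does not say which applies to MAE.
- **That neither study can be set beside published 30-day rates.** EXPAND's day-30 count uses a fixed 30-day cut-off, so this objection does not apply to it.

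**Conclusion.** The inconsistency is real and its consequence modest. PMCF 4.2 gives a 30-day event count whose end date varies by subject from day 16 to day 90. EXPAND counts the same MAE composite to day 30 in a population that includes those subjects.

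The size depends on visit timing, which is unknown in advance. For death, the German figures give 6.0% with all visits on day 60 and at most 7.5% with all on day 90, against 4.5% at day 30 (a ratio of 7.5/4.5, about 1.7). The US figures give at most 9.3% against 5.2%. These are ceilings over visit timing under the constant hazard; a hazard that fell after day 30 would raise them. Visits near day 30 make little difference, and earlier visits lower the count. The effect on the MAE composite cannot be computed from the documents.

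The APS test is unaffected. This should be corrected, but it does not threaten the study's formal conclusion.

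**What to change.** In PMCF 4.2, state that event endpoints (MAE, death, device-related events, heart failure hospitalisation) are counted by days from the index procedure, at <=30, <=180 and <=365 days, whatever visit they were reported at. Keep the by-visit rule only for measurements such as MR severity and NYHA class. This is the split Protocol 4.1 already makes.

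Add that the MAE rate is read at day 30 from the Kaplan-Meier method already planned in PMCF 9.4, with subjects censored at last contact. This also settles deaths before the visit, missed visits and events reported between visits.

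The cost is a wording change and minor re-programming. The planned Kaplan-Meier analyses and the SAP 3.2 summary of events up to 30 days already require event dates, so no new data collection is implied.

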4.3 Success Criteria

The MitraClip XTR PMCF Study will be successful if the lower one-sided 95% confidence interval (CI) of the observed APS rate for the study is greater than the Performance Goal (PG) of 80.7%.

5.0 SUBJECT SELECTION AND WITHDRAWAL

5.1 Subject Population

This study will include an analysis of male and female consented subjects from the heart failure population who satisfy the inclusion and exclusion criteria and who are treated with the MitraClip XTR System. The study will include a minimum of 220 subjects.

5.2 Subject Screening and Informed Consent

5.2.1 Subject Screening

The hospital will follow their standard of care procedures for determining if a patient is eligible for treatment with a MitraClip System. Consecutive patients who present for their procedure should be asked to provide consent for participation in the MitraClip XTR PMCF Study if they are eligible per the inclusion/exclusion criteria. Only patients that have a MitraClip XTR implanted will be included in the analysis.

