Title	Post-Market Clinical Follow-up Assessment of the Safety and Performance the MitraClip XTR System
Objectives	The primary objective of this study to evaluate the safety and performance of the MitraClip XTR System in a post-market setting.
Device	MitraClip XTR System
Targeted number of subjects	A minimum of 220 subjects
Subject Follow-up	Clinical Visit: 30 days and 12 Months Phone Call: 6 Months
Primary Endpoint	Safety and Effectiveness Acute Procedural Success (APS) defined as successful implantation of the MitraClip XTR device with resulting MR severity of 2+ or less on discharge Echocardiogram (30-day echocardiogram will be used if discharge is unavailable or uninterpretable). Subjects who die or undergo mitral valve surgery before discharge are considered to be an APS failure
Clinical Endpoints	
 • Major Adverse Event (MAE). MAE defined as a composite of all-cause Death, Myocardial Infarction, Stroke, or non-elective CV surgery for device related complications (CEC adjudicated) • MR Severity • Device Related Adverse Events (including Mitral valve stenosis, device embolization, Single Leaflet Device Attachment (SLDA), iatrogenic atrial septal defect, Myocardial perforation, or the need for mitral valve replacement instead of repair due at least in part to the MitraClip procedure or the presence of the MitraClip device)) • All-cause mortality • Recurrent heart failure hospitalization • New York Heart Association (NYHA) functional class improvement
Inclusion Criteria	
 1. Subjects scheduled to receive the MitraClip per the current approved indications for use 2. Subjects who give consent for their participation 3. Subjects with Symptomatic MR ($\geq 3+$)
Exclusion Criteria	
 1. Subjects participating in another clinical study that could impact the follow-up or results of this study.

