5.4 Subject Enrollment and Inclusion in Analysis

The patient is considered enrolled upon signing and dating an informed consent for participation. Only subjects that have an MitraClip XTR implant will be included in the analysis.

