6.0 TREATMENT AND EVALUATION OF SAFETY AND EFFICACY

6.1 Pre-treatment

Patients presenting with MR appropriate for treatment with the MitraClip will undergo screening per standard hospital procedure. If a MitraClip procedure is considered appropriate and the patient meets the screening criteria for the study (i.e. MR>3+, compliance with MitraClip approved labelling, and not participating in another study) the site shall obtain consent from the patient. The consent will permit information about the patient to be submitted to the study after successful implantation of MitraClip XTR device. No data may be entered into the study unless the informed consent is completed.

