6.2.1 Treatment Strategy or Treatment Procedures

The MitraClip procedure should be conducted in accordance with standard of care practice and approved labelling. All consented patients that have the MitraClip XTR implanted will be entered into the study.

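### The XTR PMCF tests Acute Procedural Success against 80.7% only in patients with an XTR implanted, so its implantation component is met by construction and an attempt ending without an XTR implant is not counted

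*Protocol*

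**What the plan says.** All references are to the XTR PMCF protocol in Appendix I unless marked EXPAND.

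- **Endpoint.** Section 4.1: "This is defined as successful implantation of the MitraClip device with resulting MR severity of 2+ or less upon discharge Echocardiogram", followed by "Subjects who die or undergo mitral valve surgery before discharge are an APS failure". Section 9.1 repeats the definition. The Protocol Summary words it more narrowly: "successful implantation of the MitraClip XTR device with resulting MR severity of 2+ or less on discharge Echocardiogram".
- **Success rule.** Section 4.3 requires the lower one-sided 95% confidence limit of the APS rate to be "greater than the Performance Goal (PG) of 80.7" percent. Section 9.4.1 uses an exact test in the analysis population, and section 9.3 gives a one-sided type I error of 0.05 and a minimum of 220 subjects.
- **Who is analysed.** Section 5.2.1: "Only patients that have a MitraClip XTR implanted will be included in the analysis". Section 5.4: "Only subjects that have an MitraClip XTR implant will be included in the analysis". Section 6.2.1: "All consented patients that have the MitraClip XTR implanted will be entered into the study". Section 6.1 says that consent permits "information about the patient to be submitted to the study after successful implantation of MitraClip XTR device".
- **Looser wording.** Sections 3.1, 3.2, 5.1 and 5.3, and EXPAND section 3.2, describe the set by treatment with XTR or completion of the XTR procedure. None says that a failed attempt is included.
- **Contrast.** EXPAND sections 3.1 and 5.4 analyse all attempted procedures. EXPAND section 4.2 uses the same APS definition, but with no performance goal.
- **Not visible.** The text under section 9.2, the redacted blocks in 9.3 and 9.4.1, and the derivation of 80.7%. Their absence is not criticised here.

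**The concern.** APS joins two requirements: the clip is implanted, and MR comes down. Restricting the test to patients with an XTR in place leaves the first requirement with no work to do. The excluded cases are attempts abandoned without an implant, conversions to NTR only, and deaths or mitral valve surgery before any implant. Section 4.1 would count such a death or operation before discharge as an APS failure, but the patient never enters the set.

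This is the only pass/fail test in the documents, and it serves the CE-mark follow-up requirement. Section 2.2 chose APS because it captures safety events tied to device failure as well as performance. The new feature of XTR is longer arms to help grasp the leaflets, so failure to implant is an outcome the test ought to be able to see. EXPAND will report such failures, but not against 80.7%.

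The goal's denominator matters too. Section 1.1 says the comparator is historical MitraClip data, and the history in EXPAND Appendix IV mixes denominators. If the goal is per attempt and the analysis per implanted patient, the two do not match.

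**Working it through.** **Inputs.** Goal 0.807 (section 4.3); one-sided alpha 0.05 and minimum n = 220 (9.3); exact test (9.4.1). Implant rates come from EXPAND Appendix IV: ACCESS-EU 99.6%, TRAMI 97%, REALISM high risk 96%, REALISM non-high risk 95.2%, EVEREST I and II 89%. All concern earlier devices. The XTR rate is not given, so these serve as an assumed range.

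**The plan's own figure.** The expected APS rate and power behind 220 are not visible, so 220 can be neither reproduced nor refuted. Working backwards, 220 gives 80%, 85% or 90% power at a true APS of 87.1%, 87.5% or 88.1%.

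**Pass mark.** One-sided Clopper-Pearson lower limit = 5th percentile of Beta(x, n − x + 1).
- 187/220: 0.8046, fails; P(X ≥ 187 | 0.807) = 0.0597.
- 188/220 (85.5%): 0.8096, passes; P(X ≥ 188 | 0.807) = 0.0410, the exact alpha.

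**Adding omitted failures.** With k failed attempts restored, the rate is x/(220 + k). At x = 188, k = 1 gives 188/221, lower limit 0.8055: fail (189/221, at 0.8104, would pass). The smallest k that reverses a pass:

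| Implanted-only result | k to reverse |
|---|---|
| 188/220 (85.5%) | 1 |
| 190/220 (86.4%) | 4 |
| 193/220 (87.7%) | 7 |
| 195/220 (88.6%) | 10 |
| 198/220 (90.0%) | 13 |
| 209/220 (95.0%) | 26 |

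**Expected omissions, and false-pass chance if the goal were per attempt.** Omitted attempts = 220/rate − 220. If true APS among attempts is exactly 0.807 and every non-implant is a failure, APS among implanted patients is 0.807/rate, and the implanted-only test passes with probability P(X ≥ 188) at that value.

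| Implant rate | Omitted per 220 implanted | 0.807/rate | P(pass) |
|---|---|---|---|
| 99.6% | 0.9, about 1 | 0.8102 | 5.2% |
| 97% | 6.8, about 7 | 0.8320 | 21.2% |
| 96% | 9.2, about 9 | 0.8406 | 32.4% |
| 95.2% | 11.1, about 11 | 0.8477 | 43.3% |
| 89% | 27.2, about 27 | 0.9067 | 99.5% |

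The last column applies only under the per-attempt assumption.

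**Reading the two tables together.** At the first four rates at most about 11 attempts are omitted. That reverses passes up to about 89% implanted-only APS and leaves 198/220 standing, since 13 are needed there. About 27 omissions, the 89% rate, would reverse even 209/220.

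**Denominators in the cited history.** EVEREST I: 0.709 × 55 = 39.0, so its APS of 70.9% fits 39/55 treated (inferred); among the 49 implanted it would be 39/49 = 79.6%. Asia-Pacific registry: 133/142 = 93.7%; over the 145 who underwent the procedure, 133/145 = 91.7%. The history therefore does not settle which denominator 80.7% uses.

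**The case against.** Four points on the other side carry weight.

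- **The governing definition may be hidden.** The test runs in an analysis population whose section 9.2 text is not visible, and the looser sections could be read more broadly than 5.2.1. That limits the claim to the visible wording. But no visible sentence brings failed attempts in, and a hidden definition that did so would contradict sections 5.2.1, 5.4, 6.1 and 6.2.1, so reconciliation would still be needed.
- **The verdict may well not change.** The PMCF is European. Cited European APS figures are 95.4% (Sentinel), 100% (GRASP overall; 97.8% and 100% in its subgroups) and 95.5% (the Munich cohort), and the cited European implant rates are 97% and 99.6%. At 95% APS it takes 26 omitted failures to reverse a pass, against about 1 to 7 expected. This stands, with the caveat that none of these figures is for XTR.
- **The goal may be per implanted patient.** Then alpha stays at 4.1% and what remains is a blind spot, not an error-rate problem. This stands.
- **Failed attempts are not lost.** EXPAND includes attempted procedures and follows non-implants for 30 days. True, but not against the goal.

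Two stronger readings are tempting. A reader might infer that the test cannot fail. It can: residual MR above 2+, or death or mitral valve surgery before discharge, counts as failure in implanted patients, and a patient with one XTR implanted and a further failed attempt stays in the set. A reader might also infer that the false-pass chance is 21% to 43%, or over 99%. Those figures need a per-attempt goal, which no visible text establishes.

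**Conclusion.** The structural point holds on the visible text: the implantation component of APS is inert in the PMCF primary test, and attempts ending without an XTR implant drop out of the rate altogether. This should be fixed.

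The practical effect is uncertain. A result at the pass mark is reversed by one omitted attempt. At implant rates of 95.2% to 99.6% the conclusion is exposed only when implanted-only APS is below about 89%. At 95% only the 89% implant rate of the early trials would produce enough omissions to reverse it. Type I error is inflated only if 80.7% is per attempt.

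These sizes assume 220 implanted patients, no XTR implant scored as APS failure, and implant rates borrowed from earlier devices.

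**What to change.** 1. State the denominator behind 80.7%.
2. Define one PMCF population and use it in Appendix I sections 3.1, 3.2, 5.1, 5.2.1, 5.3, 5.4, 6.1 and 6.2.1 and in EXPAND section 3.2.
3. As a minimum, prespecify a sensitivity analysis of APS in all consecutive consented European attempted-XTR procedures, with no implant counted as failure and the one-sided 95% lower limit set against 80.7%. If the goal is per attempt, make this set primary and keep the implanted-only rate as supportive.
4. Reconcile the Protocol Summary's APS wording (XTR device) with section 4.1 (MitraClip device), and report NTR-only conversions after an XTR attempt both as success and as failure.
5. Confirm that the eCRF records which device was attempted when none is implanted, and that consent covers data from non-implanted patients, since section 6.1 ties submission to successful implantation.

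**Cost.** A protocol amendment with ethics committee notice or approval, a check of consents already signed, and possibly one eCRF field. The sensitivity route costs no power.

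If the attempted set becomes primary, power falls. With 220 attempts, P(X ≥ 188) at implanted-only APS × implant rate is:
- APS 87.5% (assumed): 85% with every attempt implanted, 80% at a 99.6% implant rate, 45% at 97%.
- APS 90% (assumed): 99%, 98% and 82%; about 247 attempts would give 85% at the 97% rate.
- APS 95% (assumed): above 99% at implant rates of 95.2% or higher.

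The PMCF number is a minimum, so more European attempts can be included.
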